Unique Protocol ID: JCHP-2

Brief Title: Omega-3 Supplementation to Both Parent and Adolescent

Official Title: Omega-3 Supplementation to Both Parent and Adolescent to Reduce Behavior Problems

Document Date: May 16, 2018

Experimental Design and Methods

This section provides the design and method of the overarching study within which the three aims will be tested. We also briefly specify further programmatic goals of this line of study, and also how the specific expertise of the research team will help ensure feasibility. As with the pilot study, methodology and ultimately reporting of results will follow CONSORT 2010 guidelines (Moher et al., 2010).

Design Overview

The study design will consist of a stratified, double-blind, placebo-controlled, factorial, randomized controlled trial of children and their caregivers in a community sample in Mauritius. This closely follows the design of the pilot study (Raine et al. 2015). Unlike the pilot study however, it will utilize a 2x2 factorial design, in which children *and* their parents will be randomly assigned to either omega-3 supplementation (treatment condition) or a placebo (control condition), and will have an extended follow-up at 18 months. This results in 4 groups: (1) child and caregiver both receiving omega-3, (2) child receives omega-3, caregiver receives placebo, (3) caregiver receives omega-3, child receives placebo, (4) both parent and child receive placebo. Assessments will take place at 0 months (baseline), 6 months (end of supplementation), 12 months (6 months post-treatment), and 18 months (12 months post-treatment).

Background To The Sample and the Mauritius Child Health Project

Adolescents and caregivers will be drawn from the Mauritius Child Health Study, a multi-generational study involving three generations of subjects. Details of these three generations are provided in a cohort profile (Raine et al. 2010). Originally set up by [name] (Consultant), this longitudinal study covers early child health and development and the identification of early risk factors (including nutrition) for later psychopathology, as well as early primary prevention. Early factors that shape later cognitive functioning have also been a focus. Given the pilot findings and longitudinal data on the parents, it provides a unique platform on which to build.

Participants, Potential Attrition, and Strategies to Deal with Attrition

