Participants will consist of 400 pairs of children and their caregivers (total N = 800). This replicates cell sizes in the pilot data and allows close comparability, with 100 children and 100 adults in each of four cells. The caregivers consist of the second generation participants (their parents are the first generation) who originally comprised the birth cohort. Their adolescent children are the third generation. All caregivers have previously participated in the Mauritius Child Health Project (Raine et al., 2010). Adolescents will be aged between 11 and 18 years old, willing to participate in an RCT, and residing in the community. Exclusion criteria consist of: (1) allergy to fish or fish products, (2) use of fish oil supplementation in the past six months, (3) intellectual disability, (4) participation in the prior RCT. There are currently 1,126 children aged 11-18 years actively participating in the Mauritius Child Health Project (51.2% female; 73.2% Indian, 24.5% Creole, 2.3% other), 124 of whom took part in the prior RCT and will be excluded. Written informed consent will be obtained from the parents with assent obtained from adolescents. The study will take place in interview rooms at the project headquarters in Quatre Bornes.

Attrition is an issue in all RCTs. In our pilot data however, attrition was only 8%, even after one year, and is likely attributable both to the long-standing intergenerational relationships between our research team in Mauritius and the participants. Attrition may nevertheless be slightly more with the longer follow-up. We have three strategies to deal with attrition. First, analyses will be intention-to-treat, including all participants regardless of drop-outs. Second, we will enhance participation using staggered incentives for completion. Third, we will code for missingness and assess whether it moderates treatment outcome.

Randomization

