Aims 1 and 2 (Primary Outcome). These hypotheses will be addressed using adolescent and caregiver externalizing responses gathered at baseline and at 6, 12, and 18 month follow-ups. Responses for the adolescent will be analyzed separately from responses for the caregiver. For each separate set of responses, linear mixed effects models (Molenberghs & Verbeke, 2005) will be used to describe both the pattern of response and the within-subject covariance structure across time points. Primary analyses will not include baseline covariates, as the randomization will balance the treatment groups and eliminate selection bias. To enhance power by controlling for variability in response (Kahan et al., 2014), a small set of baseline covariates (e.g. gender, age, ethnicity) will be included in supplementary analyses.

The response may be transformed (e.g. log transformation) to reduce levels of skewness in the response to acceptable levels, as assessed by examination of residuals. Models will include binary indicators for adolescent group (omega-3 vs placebo), caregiver group (omega-3 vs placebo), and time (four level factor for times 0, 6, 12, and 18), and group by time interaction terms, as fixed effects. Time is modeled as a discrete factor to accommodate the patterns observed in our prior study (see Figure under Preliminary Data) where the omega-3 adolescent groups are similar at baseline and 6 months, and separate at 12 months. Covariance structure models (e.g. random effects, autocorrelated residuals) will be compared using information criteria in models containing all main effects and interactions of interest. Once the covariance structure has been chosen, the fixed effects will be assessed for significance using likelihood ratio tests.

Parameter estimates, standard errors, and 95% confidence intervals will be reported. In the case of a multiple degree of freedom test (e.g. group by time interaction, with 3 df), single-df contrasts will be estimated and reported, to explain the nature of the interaction.

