For the adolescent, Hypothesis 1a will be addressed using a child group by time interaction term (time trends for omega-3 and placebo group need not be parallel), or a child group main effect if the interaction term is non-significant (parallel time trends). Similar models will address the corresponding Hypothesis 1b for the caregiver responses. For both the adolescent and caregiver responses, Hypothesis 2a will be tested by an adolescent group by caregiver group by time interaction, or by an adolescent by caregiver interaction if the four adolescent by caregiver group trends are parallel.

Aim 3 (Secondary Outcome). Working hypothesis 3a (change in neurocognitive and academic factors) will be tested using the same mixed effects models as outlined above in aims 1 and 2. Working hypothesis 3b (mediation), whether improvement in neurocognitive variables (e.g. impulse control) or academic WRAT scores partly account for the treatment effect on child behavior will be assessed using mediation analyses. Based on the prior study (Raine et al, 2015), effects of supplementation should emerge by the 12-month time point. Analyses will test whether changes in risk factors between baseline and the 6 month point mediate the 12-

month treatment effect. These analyses will be conducted using the PROCESS SPSS macro (Hayes, 2012), which will also be used to assess moderated mediation (e.g. neurocognitive measures mediate outcomes more strongly in younger adolescents). To test significance of the indirect effects (i.e. mediation), bias-corrected confidence intervals for the indirect effects will be generated using 10,000 bootstrap samples. To assess extent of mediation, the reduction in variance explained in treatment outcome by the intervention after controlling for improved parental behavior (the mediator) will be calculated in a two-step regression. Equivalent analyses will be performed for the other neurocognitive variables.

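### The H3b mediation analysis names neither its exposure arm nor the caregiver arm, so a one-treatment model run from the text could report false mediation if the caregiver drink shifts both the child's mediator and outcome

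*Combined protocol and SAP*

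**What the plan says.** Under Design Overview, the combined protocol and SAP says of the trial that "it will utilize a 2x2 factorial design", with child and caregiver each allocated to omega-3 or placebo.

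Under Statistical Methods, the text for Aims 1 and 2 puts both factors in the model: "Models will include binary indicators for adolescent group (omega-3 vs placebo), caregiver group (omega-3 vs placebo". For the adolescent's own responses it goes further: "Hypothesis 2a will be tested by an adolescent group by caregiver group by time interaction". Under Aim 3, H3a (neurocognitive and academic change) is to be "tested using the same mixed effects models as outlined above in aims 1 and 2", so it also carries both arms.

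H3b, in the same Aim 3 paragraph, does not repeat this. It asks whether the 0-6 month change in a neurocognitive or WRAT measure mediates the 12-month effect on child behavior, and says: "These analyses will be conducted using the PROCESS SPSS macro". Significance rests on a bias-corrected bootstrap interval with 10,000 resamples. Treatment and intervention appear only in the singular. No exposure arm is named, no covariates are listed, and the caregiver arm is not mentioned. The sentence on the extent of mediation gives better parental behavior as the mediator, although H3b's stated mediators are neurocognitive and academic.

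**The concern.** Randomization makes the caregiver arm independent of the child arm. Leaving it out therefore does not bias the total effect of the child drink or the path from child arm to mediator. The mediator itself is not randomized, so the mediator-to-outcome path has no such protection. If the caregiver drink changes both the child's 6-month mediator and the child's 12-month behavior, it is a common cause of the two, and the mediator-to-outcome slope absorbs it. Adjusting for baseline values does not help, because any caregiver effect arises after baseline.

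The trial could then report that a cognitive or academic gain carries the effect of the child's drink when the mediator does nothing. Unlike most confounders of this path, this one is randomized and fully recorded, so its bias can be removed completely.

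**Working it through.** The documents state no effect size, power or error rate for H3b, so there is no figure of the plan's own to reproduce.

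**Inputs from the documents.** Participants section: "with 100 children and 100 adults in each of four cells", so 4 × 100 = 400 pairs. Pilot "attrition was only 8%, even after one year", so 400 × 0.92 = 368 as a sensitivity value. A 95% interval is stated for Aims 1 and 2 and is assumed to carry over to H3b.

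**Assumptions.** Residual SD of 1, a balanced 2x2, and no true mediator-to-outcome effect. Let *a* be the child-drink effect on the mediator, and *cm* and *cy* the caregiver-drink effects on mediator and outcome, all in SD units.

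**Step 1: closed form, caregiver arm omitted.** A balanced 0/1 arm has variance 1/4, so

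bias in slope = (cm·cy/4) / (1 + cm²/4)

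With cm = cy = d, SE = √[(1 + d²/4 − bias²(1 + d²/4)) / (n(1 + d²/4))].

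At d = 0.5 and n = 400: bias = 0.0625/1.0625 = 0.0588 and SE = √(1.0588/425) = 0.0499. The ratio is 1.18, so a two-sided 5% test rejects a true zero slope 21.8% of the time.

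| d | bias | SE (n=400) | false rejection, n=400 | n=368 |
|---|---|---|---|---|
| 0.2 | 0.0099 | 0.0500 | 5.4% | 5.4% |
| 0.3 | 0.0220 | 0.0500 | 7.2% | 7.1% |
| 0.4 | 0.0385 | 0.0500 | 12.0% | 11.4% |
| 0.5 | 0.0588 | 0.0499 | 21.8% | 20.4% |

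**Step 2: the planned type of interval.** The bias-corrected bootstrap for the indirect effect was simulated with 1,000 trials per setting, 1,000 resamples and a direct child-arm effect of 0.3 SD. Both models were fitted to the same simulated data. The table gives the rate of falsely declared mediation.

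| n | a | cm, cy | arm omitted | arm included | difference (points) |
|---|---|---|---|---|---|
| 400 | 0.3 | 0, 0 | 7.1% | 7.3% | −0.2 |
| 400 | 0.3 | 0.2, 0.2 | 6.0% | 6.4% | −0.4 |
| 400 | 0.3 | 0.3, 0.3 | 8.8% | 7.5% | 1.3 |
| 400 | 0.3 | 0.5, 0.5 | 23.0% | 7.0% | 16.0 |
| 400 | 0.5 | 0.2, 0.2 | 6.6% | 6.7% | −0.1 |
| 400 | 0.5 | 0.3, 0.3 | 10.4% | 8.1% | 2.3 |
| 400 | 0.5 | 0.5, 0.5 | 26.1% | 5.8% | 20.3 |
| 368 | 0.3 | 0.3, 0.3 | 8.7% | 6.5% | 2.2 |
| 368 | 0.5 | 0.5, 0.5 | 25.5% | 7.2% | 18.3 |
| 400 | 0.3 | 0.5, −0.5 | 25.5% | 7.8% | 17.7 |
| 400 | 0.3 | 0.5, 0 | 5.7% | 6.6% | −0.9 |
| 400 | 0.3 | 0, 0.5 | 6.9% | 7.6% | −0.7 |
| 400 | 0 | 0.5, 0.5 | 2.0% | 0.7% | 1.3 |

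The Monte Carlo standard error of a rate is about 0.7-1.4 points for most rows. With opposite-sign caregiver effects the false indirect effect reverses sign. With the arm included, the mean indirect effect lies between −0.001 and +0.001.

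**Step 3: cross-check.** A simpler test requires both paths to be significant at 5% (400 children, a = 0.4, 6,000 trials). With the arm omitted it gives 5.1%, 7.2%, 11.9% and 19.8% at d = 0.2, 0.3, 0.4 and 0.5. With the arm and the product included it gives about 5%.

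**The case against.** The strongest reply is that the plan has not excluded the caregiver arm. H3b follows directly on H3a, which carries both arms, and an analyst might carry them over. The reference to parental behavior as a mediator even fits a reading in which the caregiver drink, or the whole 2x2 allocation, is the exposure. This stands as far as it goes: the omission is inferred from silence. But a text that leaves both exposure and covariates open, and speaks of one intervention, can readily be run as a one-treatment model.

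A reader might also infer several stronger things that the documents do not support:

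- **That H2a predicts this confounding.** H2a concerns externalizing responses. No section predicts that the caregiver's drink changes the child's CANTAB or WRAT scores by 6 months, and an effect on the outcome alone produces no inflation.
- **That the interaction sought in H2a makes the bias much worse.** In the both-paths test, with caregiver effects of 0.25 SD and a = 0.3, a centred interaction of 0.2 or 0.3 SD in both variables gives 5.4% or 6.5%, against 4.9% with none. An uncentred 0/1 product gives 9.7% or 14.3%, but mostly because it raises the average caregiver effect to 0.25 + 0.2/2 = 0.35 or 0.25 + 0.3/2 = 0.40 SD.
- **That caregiver effects on both variables are sufficient.** The child drink must also move the mediator. With a = 0 the rate stays below 5%.
- **That everything above 5% comes from the omission.** The bias-corrected bootstrap runs at about 6-8% with the arm included whenever a is not zero.

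Finally, nothing in the documents supports a caregiver effect as large as 0.5 SD on the child's cognition. That end of the range is an assumption.

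**Conclusion.** The point holds as a gap in specification with a real but conditional consequence. H3b does not state its exposure or account for the second randomized arm, although the plan's other models of the same child variables do. Harm requires three things together: a one-treatment model, a caregiver-drink effect on both the 6-month mediator change and the 12-month outcome, and a child-drink effect on the mediator. Under equal assumed caregiver effects the excess is negligible at 0.2 SD or below, about 1-2 points at 0.3 SD and about 15-20 points at 0.5 SD. These sizes rest on unit residual SDs, 368-400 children and no true mediator-to-outcome effect. The matter is minor: H3b is a secondary working hypothesis, and the Aim 1 and 2 analyses are untouched.

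**What to change.** In the Aim 3 text, name the exposure for H3b: the child arm, if the question is how the child's drink works. Enter the other randomized arm and the centred child-by-caregiver product as covariates in both the mediator and the outcome equations in PROCESS. Do the same in both steps of the two-step regression and in the moderated-mediation models. Reconcile the mediator named in the two-step sentence with H3b's own list. If parental behavior is intended there, the caregiver arm bears on it more directly and the adjustment matters more.

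The cost is a sentence or two of wording and about 2 degrees of freedom out of roughly 400. No new data are needed.

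### Extent of mediation is to be measured by a drop in variance explained, which is not the mediated share of the treatment effect and, read as a relative drop in incremental R-squared, overstates it

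*Combined protocol and SAP*

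**What the plan says.** The combined document, Statistical Methods, Aim 3 (Secondary Outcome), asks under working hypothesis 3b whether improvement in neurocognitive variables or academic scores may "partly account for the treatment effect on child behavior will be assessed using mediation analyses". The mediator is change from 0 to 6 months and the outcome is the treatment effect at 12 months.

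Two separate quantities are planned.

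- **Significance.** The plan says that "bias-corrected confidence intervals for the indirect effects will be generated using 10,000 bootstrap samples", using PROCESS.
- **Extent.** The plan says: "To assess extent of mediation, the reduction in variance explained in treatment outcome by the intervention after controlling for" improved parental behavior, which it labels the mediator, and that this "will be calculated in a two-step regression". It adds: "Equivalent analyses will be performed for the other neurocognitive variables".

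This is the only measure of extent in the plan. It has no formula and no interval. The text does not say whether the reduction is divided by the step-one R-squared, or whether R-squared is semi-partial or partial. It never calls the result a share or proportion.

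**The concern.** Hypothesis 3b is about partial mediation, so the natural follow-up is how much of the benefit runs through the risk factor. The treatment effect is a difference in means. Variance explained by treatment is proportional to the square of that difference. A reduction in variance explained therefore answers a different question, and a reader who takes it as the part of the benefit that is mediated will usually take too large a number. The gap is widest in relative terms when mediation is small to moderate, which is the situation that the hypothesis expects.

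At stake is a descriptive figure for a secondary aim. It could nevertheless become the headline statement on mechanism.

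**Working it through.** The plan states no mediated share, R-squared or effect size, so there is no figure of its own to reproduce.

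**Inputs from the document**
- 400 adolescents, 200 against 200 on the child factor (Participants section).
- 8% attrition in the pilot, giving 400 × 0.92 = 368.

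**Assumed inputs**
- Mediated share m, from 0 to 100%.
- Treatment effect on the mediator, 0.1 to 0.5 SD (0.3 SD with 1:1 allocation gives a treatment-mediator correlation r of about 0.15).
- Total effect on outcome, 0.2 to 0.5 SD.

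**Formula.** Let X be treatment, Y the outcome, c the total effect, c′ the direct effect, and m = 1 − c′/c.
- Treatment alone: R² = c² Var(X)/Var(Y).
- Increment for treatment after the mediator: c′² Var(X)(1 − r²)/Var(Y).
- Relative drop: 1 − (c′/c)²(1 − r²) = 1 − (1 − m)²(1 − r²).

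With r near 0 this is m(2 − m), so the inflation factor is 2 − m.

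**Relative drop in incremental R-squared**

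| True share m | r near 0 | Factor | r = 0.15 (1 − r² = 0.9775) |
|---|---|---|---|
| 10% | 19% | 1.9 | 1 − 0.81 × 0.9775 = 20.8% |
| 20% | 36% | 1.8 | 1 − 0.64 × 0.9775 = 37.4% |
| 30% | 51% | 1.7 | 1 − 0.49 × 0.9775 = 52.1% |
| 50% | 75% | 1.5 | 1 − 0.25 × 0.9775 = 75.6% |
| 100% | 100% | 1.0 | 100% |

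The result is not sensitive to the assumed mediator effect. From 0.1 to 0.5 SD, a true 30% reads as 51.1% to 53.9%, and a true 10% as 19.2% to 23.8%.

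**Simulation.** With 368 adolescents and effects of 0.3 SD on both mediator and outcome, the medians were 20.1%, 36.8%, 52.0% and 74.5% for true shares of 10, 20, 30 and 50%. At a true 30%, the 5th to 95th percentiles ran from 22% to 88%.

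**No mediation (m = 0).** The population value is r²: 0.15² = 2.25%, rising to 5.9% with 0.5 SD on the mediator.

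**Partial R-squared.** Here the increment is divided by the variance that the mediator leaves unexplained.
- At 0.3 SD on both, true shares of 10, 20, 30 and 50% give 19.6%, 34.3%, 46.8% and 66.9%.
- At 0.2 SD on the mediator and 0.5 SD on the outcome, a true 20% gives 14.7% and a true 30% gives −10.2%.

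**Absolute drop.** At 0.3 SD on both and a true 30%, R-squared falls by 0.0115 from 0.0220. That number conveys extent only when divided by 0.0220, and 0.0115/0.0220 = 52% returns the inflated figure.

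**The case against.** The strongest reply is that the plan never promises a share. It promises a reduction in variance explained, and an absolute fall of about 0.01 would not be mistaken for a percentage of benefit mediated. This stands as far as it goes: the inflation factors belong to one reading, a relative drop in incremental R-squared, and must be stated as conditional. It does not rescue the sentence. The absolute figure does not express extent, and the partial version has an error whose sign depends on unknown inputs. Leaving the choice open also allows it to be made after the data are seen.

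Four stronger conclusions are tempting, and the documents do not support them.

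- **That the measure doubles the mediated share in general.** The factor is close to 2 only for small shares and falls to 1 at full mediation.
- **That any modest mediator would appear to explain half the benefit.** A true 10% reads as about 21% and 20% as about 37%. Reaching half takes a true share near 30%.
- **That the measure manufactures mediation where there is none.** The offset is about 2% at r = 0.15. The simulated 5th to 95th percentile range of −19% to +23% with no mediation is mostly sampling noise.
- **That hypothesis 3b is wrongly tested.** The test is the bootstrap interval for the indirect effect ab. That interval is on the effect scale and is untouched.

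It is also fair to say that the usual alternative, ab/c, is imprecise. In simulation with the same inputs, a true 30% gave estimates from about 13% to about 70%. That is a reason to put ab and c first and to show an interval for any ratio. It is not a reason to use a measure centred on the wrong value.

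**Conclusion.** The concern holds in a limited form. The planned measure of extent is on the squared-effect scale, is incompletely defined, and is not the mediated share. If it is reported as a relative drop in incremental R-squared, which is the natural product of a two-step regression, it overstates the share by a factor of about 1.5 to 2 for shares up to half. The algebra needs only a linear model. The worked figures rest on assumed values of m and r, because the documents give none, but they change little over the range tried. Under partial R-squared, no fixed direction of bias can be claimed.

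The same sentence has a plainer defect that needs no assumed figures. It names improved parental behavior as the mediator, while hypothesis 3b names neurocognitive and academic variables. These must be reconciled before any measure of extent can be computed.

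This should be changed, but it does not threaten the primary analysis or the test of mediation.

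**What to change.** Replace the two-step sentence with text to this effect:

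- For each mediator, extent is reported as the indirect effect ab, in outcome units, with the bootstrap interval already planned, beside the total effect c and its interval.
- If a share is also wanted, ab/c is reported with a bootstrap interval and a statement that it is imprecise at this sample size. Showing c with its interval lets the reader see when the denominator is close to zero.
- No R-squared reduction is presented as the mediated share.
- The mediators are named, and the reference to parental behavior is either reconciled with hypothesis 3b or set out as its own mediation question.

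The cost is a rewritten sentence or two. PROCESS already gives ab, c and c′, and no new data are needed. The downside is presentational: the reported extent will look smaller, and any share will carry a wide interval.

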Participants will be randomized into four groups using urn randomization, a covariate adaptive randomization method (Wei & Lachin, 1988). Adaptive randomization is employed because it protects the study from bias while promoting study objectives, it improves power over standard designs, and it balances assignment of treatment across covariates in a way superior to traditional stratification (Rosenberger et al., 2012). We aim to achieve balanced groups on three main child covariates: age, gender, and ethnicity. An advantage of the Mauritius cohort is that we have data on the parents' externalizing behavior over the life-course (Raine et al. 2010) which we could add as a fourth covariate to further ensure that groups are balanced.

Omega-3 Intervention

Omega-3 supplementation. As in the pilot study, this consists of a 200 ml drink. The base drink in both treatment and placebo conditions consists of fruit juice containing vitamin D (0.85 micrograms) and antioxidants (ferric reducing ability of plasma value of 0.71 mmol/100g). For the treatment condition only, 1660 mg of omega-3 (550 mg of DHA, 550 mg of EPA, 560 mg of alpha-linolenic acid) is added to the base drink. Placebo drinks are matched exactly with the fish-oil drink in terms of size, appearance, and flavor. Caregiver and child drinks are differentially color-coded.

This drink is chosen because: (i) it contains a higher dosage of omega-3 than standard capsules in a small liquid quantity (60.6% of a standard can of cola) suitable for child / adolescent consumption, (ii) the fruit-flavored drink may be better tolerated and result in higher compliance with children than fish-oil capsules.

Treatment duration and administration. As in the pilot study, treatment duration will be six months. It was chosen because prior studies have usually been 2 - 4 months (Sinn et al., 2010), and a longer duration may be more effective in producing longer-term behavioral change. The drink will be administered by the parents to their children at any time each day.

Primary Outcome Measures

The pre-defined primary outcome measures are externalizing behavior problems. Secondary outcomes included internalizing behavior problems and neurocognitive / academic mediators. We include additional *secondary* measures of reactive-proactive aggressive behavior and callous-unemotional traits to replicate the pilot findings and explore antisocial subtypes (the pilot data showed stronger effects for reactive aggression).

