Other measures of antisocial behavior taken in the pilot data will be repeated here to assess replicability of original findings. These include the *Reactive and Proactive Aggression Questionnaire* (RPQ), Developed by the PI, this instrument assesses two overlapping yet distinct forms of aggression (Raine et al., 2006). *Psychopathic-like traits* will be assessed by caregivers using the Antisocial Personality Screening Device (APSD) consisting of three sub-scales: callous-unemotional traits, narcissism, and impulsivity (Frick et al., 2000). Due to the introduction of callous-unemotional traits in DSM as a specifier for conduct disorder, adolescents will also complete the Inventory of Callous-Unemotional Traits (ICU - Essau et al., 2006). In caregivers, psychopathy will be assessed using the self-report *Psychopathic Personality Inventory* (PPI - Lilienfeld & Andrews, 1996). These measures also showed significant changes in the pilot study.

Secondary Outcome Measures

Neurocognitive Risk Factors. These encompass cognition, emotion, and motor functioning and will be assessed using the CANTAB (Robbins et al., 1994). This battery is selected because it is language and culture independent, has been extensively validated on children and adolescents, and its user-friendliness to adolescents helps assure feasible implementation. Measures are selected based on the most pertinent neurocognitive domains relevant to antisocial / aggressive behavior (e.g. Ogilvie et al. 2011; Raine et al., 2005; Cauffman et al., 2005), including attention (Attention Switching Task), cold executive functioning (Stockings of Cambridge), hot executive functioning (Cambridge Gambling Task), emotional decision-making (Affective Go/NoGo), social / emotional cognition (Emotion Recognition Task), and impulse control (Stop Signal Task). Minimal reading (2 tasks) or no reading (4 tasks) is needed.

Academic Skills. As per C2's recommendation for "expanded assessment" to cover other domains, academic skills will be assessed using the Wide Range of Achievement Test (WRAT-4 – Wilkinson & Robertson, 2006) which provides measures of mathematics, spelling, sentence completion, and word reading. Mauritian children today are fluent in English which is the oral and written language of instruction from age 5.

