The parent (CBCL) and youth (YSR) reports also include School Competence scales, while the teacher (TRF) form includes Academic Performance and Adaptive Functioning (Achenbach et al., 2015). These will extend the scope on mechanistic processes beyond neurocognitive functioning.

As in the pilot study, parental belief in treatment allocation to the omega-3 group (yes, no) will be measured at the end of treatment to assess influence on behavioral change. Demographics will again be collected on entry into the study, together with an adverse events questionnaire at the end of treatment.

Adherence to protocol and blood assays.

Adherence to the treatment regimen is a frequent problem in RCTs. As before, this will be assessed by assays of omega-3 from finger-prick blood taken from both caregiver and adolescent at all four time-points, with microwave irradiation assays conducted by team member [name] an NIAAA. For full methodological details see Lin, Loewke, Hyun, Leazer, & Hibbeln (2012). In response to C2, blood will additionally be assessed mid-way through supplementation (3 months). To help further enhance adherence, participants will be called every two weeks to remind them to use supplements, and to assess frequency of drink consumption by caregiver and adolescent in that time period (number of drinks / two weeks). To further facilitate compliance, participants will be given a bonus payment if their % blood omega-3 levels have risen higher than the bottom quartile of the population.

Statistical Methods

Overview. An intention-to-treat (ITT) design using all randomly assigned participants will be employed for all data analyses. All data will be blindly double-entered and checked for consistency.

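### The extent-of-mediation step for Hypothesis 3b names parental behavior as the mediator, which H3b does not, and does not expressly cover the WRAT scores

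*Combined protocol and SAP*

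**What the plan says.** All the operative text is in one block, Statistical Methods, Aim 3 (Secondary Outcome).

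- **Hypothesis.** H3b asks "whether improvement in neurocognitive variables (e.g. impulse control) or academic WRAT scores partly account for the treatment effect on child behavior".
- **Timing.** The analyses test "whether changes in risk factors between baseline and the 6 month point mediate" the treatment effect at 12 months.
- **Significance.** Indirect effects are tested with the PROCESS macro, using bias-corrected intervals from 10,000 bootstrap samples.
- **Extent.** The reduction in outcome variance explained by the intervention "after controlling for improved parental behavior (the mediator) will be calculated in a two-step regression".
- **Scope of the extent step.** "Equivalent analyses will be performed for the other neurocognitive variables".

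Elsewhere, Primary Outcome Measures gives the secondary outcomes in one line: "Secondary outcomes included internalizing behavior problems and neurocognitive / academic mediators". Secondary Outcome Measures describes the CANTAB under Neurocognitive Risk Factors and the WRAT-4 under a separate heading, Academic Skills. Caregiver externalizing behavior appears under Aims 1 and 2 as a primary response, analysed separately from the adolescent's.

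**The concern.** The words in parentheses label parental behavior as *the* mediator, so it cannot be taken as a covariate or an aside. H3b, a few sentences earlier, gives a different list. An analyst who follows the extent sentence literally puts a caregiver measure into the second step of the regression and reports how much of the child's treatment effect it absorbs. That is a different question from H3b. It is also a delicate one here, because caregivers are themselves randomized to omega-3 or placebo in the 2x2 design and their externalizing behavior is a primary response.

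The sentence that follows speaks of the *other* neurocognitive variables, as though the variable just named were neurocognitive, which parental behavior is not. It also leaves open whether the academic half of H3b gets an extent figure at all.

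At stake is how fully the size of mediation is pre-specified. The step names no scale or rater for parental behavior, and it does not say which H3b variable that phrase stands in for. Part of the analysis would have to be settled outside the plan.

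**Working it through.** The plan states no extent-of-mediation figure, so there is nothing to reproduce. The check compares passages.

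**1. What the step computes.** On the usual reading of a two-step regression, let Y be the 12-month child outcome, T the treatment and M the mediator.

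- Variance explained by treatment alone: R²(T).
- Variance that treatment adds once the mediator is in the model: R²(M, T) − R²(M).
- Extent of mediation: R²(T) − [R²(M, T) − R²(M)].

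Every term except R²(T) depends on M. Changing M therefore changes what is estimated, not just how it is labelled.

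**2. Which M each part of the plan supplies.**

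| Place | Mediator |
|---|---|
| Aim 3, H3b | Neurocognitive variables, or WRAT scores |
| Aim 3, timing sentence | Baseline-to-6-month change in risk factors |
| Primary Outcome Measures | Neurocognitive and academic mediators |
| Aim 3, extent sentence | Improved parental behavior |
| Aim 3, follow-on sentence | The other neurocognitive variables |

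Only the extent sentence names parental behavior.

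**3. Whether another place reconciles them.** Caregiver behavior is measured (Primary Outcome Measures) and modelled (Aims 1 and 2), but always as an outcome. The mediators described under Secondary Outcome Measures are neurocognitive and academic. Nothing in the document gives parental behavior a mediating role.

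**4. What the follow-on sentence reaches.** It expressly covers the neurocognitive variables, so these do get an extent figure. It does not mention WRAT. Three places treat academic measures as a class of their own: H3a, which pairs neurocognitive with academic factors; H3b, which joins the two with *or*; and the separate headings for CANTAB and WRAT-4. On that usage WRAT falls outside the sentence, although the sentence is loosely worded.

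**5. What is not affected.** The bootstrap sentence is not limited to neurocognitive variables, so indirect effects through WRAT are still tested. The Aims 1 and 2 models and the planned 400 pairs do not depend on the extent step.

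**The case against.** **The follow-on sentence may include WRAT.** By speaking of *other* neurocognitive variables straight after parental behavior, the sentence is already using the term loosely. A generous reader could take it to mean the rest of the H3b set. This stands in part. A reader might infer that WRAT is definitely excluded, but the text supports only that it is not expressly covered. The remark "These will extend the scope on mechanistic processes beyond neurocognitive functioning" does not settle it either, because it is said of the CBCL, YSR and TRF school scales and not of the WRAT.

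**A count of the gap.** A reader might set the six CANTAB tasks against the four WRAT-4 measures and report the share left without a figure. The documents do not support that. It relies on the strict reading just described, and it counts tasks, whereas a task may yield several scores and the plan does not say which scores enter the mediation models.

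**Parental behavior is not wide open.** A reader might infer that the term could mean any of several caregiver instruments. The natural default is caregiver externalizing behavior, which the plan already measures and analyses, and the timing sentence supplies the change window. What is missing is an explicit scale and rater.

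**The aims may say more.** The document refers to three aims whose full wording is not in it, and a parental-mediation hypothesis could be stated there. This limits the point to H3b as printed. It does not cure the mismatch, because the extent sentence stands under that hypothesis.

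**It is only a wording slip.** It may be. The text cannot show whether the phrase is a leftover or a mediator omitted from H3b. Either way it stands in the sentence that tells the analyst what to compute.

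**Conclusion.** The mismatch holds. As printed, the extent-of-mediation step controls for a variable that H3b does not name as a mediator and that no other part of the document treats as one. Confidence in this is high. That the WRAT scores may be left without an extent figure is held with moderate confidence, since it depends on reading *neurocognitive* as the rest of the document uses it.

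The point is minor. It affects one descriptive quantity in a secondary aim, and the neurocognitive variables are still reached through the follow-on sentence. A reader might infer that the mediation analysis as a whole is aimed at the wrong variable, but the bootstrap test of indirect effects follows from H3b and is unaffected, as are the primary analysis and the sample size. No numerical size can be given.

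The conclusion assumes that H3b as printed in Aim 3 is the governing statement of the hypothesis.

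**What to change.** The sponsor should say which mediators are meant and make the step and H3b agree.

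- **If parental behavior is not intended:** in the extent sentence, replace the reference to it with *the baseline-to-6-month change in the mediator*, and replace the follow-on sentence with *The same calculation will be made for each neurocognitive variable and each WRAT score.*
- **If it is intended:** add it to H3b as a mediator with its scale and rater, confirm that the baseline-to-6-month window applies, and still apply the extent step to each neurocognitive variable and each WRAT score.

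The cost is two sentences in the first case, plus one line in H3b in the second. No new data are needed, and the design, sample size and primary analysis stay as they are.
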